1. Using the geometric mean measured exposed individual based on study 201544 (200 µg top dose Day 1) to generate (linear extrapolation including an increase of 1.71 fold for C_{max} and 1.54-fold on AUC due to formulation differences) the exposure for a 1000 µg Inhaled dose concomitant with a 10 mcg intravenous dose (15 min infusion) (intravenous dose exposures assume 1% of inhaled exposure as worst case) based on a single dose period 1 and following a single oral dose of 800 µg in period 2 (assuming 60:40 lung to oral deposition using study data from 201544 and charcoal block and linear extrapolation). C_{max} and AUC_{0-24h} of 3.5 ng/mL and 14.7 ng.h/mL for Period 1 and a C_{max} and AUC_{0-24h} of 0.47 ng/mL and 3.7 ng.h/mL for Period 2 respectively.
2. Based on the no observed adverse event level (NOAEL) derived from the rat 3 month toxicology study R29876 with a C_{max} and AUC of 43.7 ng/mL and 286 ng.h/mL respectively.
3. Based on the highest achieved geometric mean value derived from reported trials to date of 5.3 ng/mL and 85 ng.h/mL based on exposure on Day 7 following repeat daily single doses (study PII115117).

For more detailed information on the clinical pharmacokinetics, see the GSK2269557 IB [GlaxoSmithKline Document Number [2012N141231_07](#)].

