
 
To generate samples that will be used to characterise the metabolic profile of GSK2269557 in plasma, urine, faeces, and duodenal bile (following IV dose only), following a single IV microtracer of [C]-GSK2269557 (concomitant with an inhaled non-radiolabelled dose) and a single oral dose of [C]-GSK2269557 (these analytical investigations will be conducted and the results reported under a separate Platform Technology Services (PTS) In vitro/In vivo Translation (IVIVT), GlaxoSmithKline protocol).
 
	
 
Characterisation and quantification of metabolites in plasma, urine, faeces, and duodenal bile (these analytical investigations will be conducted and the results reported in a separate GSK PTS IVIVT protocol).
 

1. For measured concentrations of GSK2269557 in blood plasma, the nomenclature [C]-GSK2269557 describes the parent GSK2269557 concentration derived via analysis by liquid chromatography (LC) + Accelerator Mass Spectrometry (AMS), whereas GSK2269557 describes the parent GSK2269557 concentration derived via liquid chromatography-tandem mass spectrometry (LC/MS).

Note: the above table is as presented in the protocol amendment, subsequently additional PK parameters have been requested including: plasma AUC(0-24) and %AUCex for parent GSK2269557 and total radioactivity analytes; plasma ML(iv), ML(po), Fg, EH, Fabs; parent GSK2269557/ total radioactivity ratios for the plasma PK parameters Cmax, AUC(0-t), AUC(0-24) and AUC(0-∞); and CLR derivations are described in Section 8.

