ML(iv)	
Metabolite load following intravenous administration is calculated as:
 $\frac{\text{Total Radioactivity AUC}(0-\infty) - [\text{14C}]\text{-GSK2269557 AUC}(0-\infty)}{\text{Total Radioactivity AUC}(0-\infty)}$ 
Treatment period 1 only

ML(po)	
Metabolite load following oral administration is calculated as:
 $\frac{\text{Total Radioactivity AUC}(0-\infty) - \text{GSK2269557 AUC}(0-\infty)}{\text{Total Radioactivity AUC}(0-\infty)}$ 
Treatment period 2 only.
 
Note: GSK2269557 AUC(0-∞) may be updated depending on the sample analysis conducted but refers to the parent GSK2269557 from oral dose.

Fg	
Fraction metabolised by gut wall as a fraction of the oral dose will be calculated as follows:
 $Fg = 1 - (ML(po) - ML(iv))$
E H	
Hepatic extraction ratio is calculated (Davis, B et al, 1993) as follows:
 $E_H = CL(iv)/1450 \text{ mL/min}$
F abs	
Fraction absorbed following an oral dose is calculated as follows:
 $F_{abs} = \frac{\text{Oral F}(0-\infty)}{1 - E_H} / F_g$
Dose(IV)	Radiometric IV dose will be calculated by Covance
Dose(oral)	Radiometric Oral dose will be calculated by Covance
Dose(inhaled)	Nominal inhaled dose
Oral F (0-∞)	
Oral absolute bioavailability based on AUC(0-∞) calculated as:
 $\frac{\text{GSK2269557 AUC}(0-\infty)(\text{oral})}{\text{Dose}(\text{oral})} / \frac{[\text{14C}]\text{-GSK2269557 AUC}(0-\infty)(\text{iv})}{\text{Dose}(\text{iv})}$ 
Per subject.
 
Note: Radiometric dose will be used for oral and iv as described in Table 1. GSK2269557 AUC(0-∞)(oral) may be updated depending on the sample analysis

Parameter	Parameter Description
	conducted but refers to the parent GSK2269557 from oral dose.
Inhaled F (0-∞)	
Inhaled absolute bioavailability based on AUC(0-∞) calculated as
 $\frac{\text{GSK2269557 AUC(0-∞) (inhaled)}}{\text{Dose (inhaled)}} \Bigg/ \frac{[14\text{C}]\text{-GSK2269557 AUC(0-∞) (iv)}}{\text{Dose (iv)}}$ 
Per subject.
 
Note: Radiometric dose will be used for oral and iv as described in Table 1.

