### 8.3.2. Summary Measure

A secondary objective is to determine parent GSK2269557 concentration in plasma following a single IV microtracer of [C]-GSK2269557 (concomitant with an inhaled non-radiolabelled GSK2269557 dose) and a single oral dose of [C]-GSK2269557. To assess this, the plasma PK parameters: AUC (0-inf), AUC (0-t), AUC (0-24), %AUCex, Cmax, tmax, t1/2 of parent GSK2269557 ([C]-GSK2269557 and GSK2269557) will be summarised and listed and the volume (Vdss and Vc) and clearance of parent GSK2269557 ([C]-GSK2269557) after IV dose only will be summarised and listed.

Another secondary objective is to estimate the absolute bioavailability of GSK2269557 following inhaled and oral administration. To assess this, the oral and inhaled bioavailability (F) will be summarised and listed.

To assess metabolism, the plasma PK parameters: ML(iv), ML(po), Fg, EH, Fabs will be summarised and listed. To assess exposure and metabolite ratio in humans, the ratio of Parent GSK2269557/total radioactivity will be calculated for the plasma PK parameters: Cmax, AUC(0-t), AUC(0-24) and AUC(0-∞), results will be summarised, listed and statistical analyses will be conducted as described in Section 8.3.4.1. To assess renal clearance, the PK CLr will be summarised and listed if bioanalysis can quantify parent GSK2269557 in urine collection intervals (i.e. if Ae is quantifiable for collection intervals).

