2.14.	PK	PK06	Summary of Metabolic, Hepatic Extraction and Absorption Parameters	
Refer to Section 11.4.3 for parameters that should be log transformed.
 
Include PK Parameters: ML(iv), ML(po), Fg, EH and Fabs
	SAC

Pharmacokinetic: Tables					
No.	Population	IDSL / TST ID / Example Shell	Title	Programming Notes	Deliverable
2.15.	PK	[Non-Standard] Refer to Programming notes	Summary of Parent GSK2269557/Total Radioactivity Ratio for Cmax, AUC(0-24), AUC(0-∞) and AUC(0-t)	Include columns for: period, parent GSK2269557/total radioactivity ratio (GSK2269557/total radioactivity or 14C-GSK2269557/ total radioactivity), parameter (Cmax, AUC(0-24), AUC(0-∞) or AUC(0-t)), geometric mean for ratio, SD(log), 95% CI, median, minimum, maximum and between subject geometric coefficient of variation (CVb (%)).	SAC
2.16.	PK	[Non-Standard] Refer to Programming notes	Summary of Statistical Analyses for Parent GSK2269557/Total Radioactivity Ratio for Cmax, AUC(0-24), AUC(0-∞) and AUC(0-t)	Include columns for: period, parent GSK2269557/total radioactivity ratio (GSK2269557/total radioactivity or 14C-GSK2269557/ total radioactivity), parameter (Cmax, AUC(0-24), AUC(0-∞) or AUC(0-t)), estimate for ratio, SD(log) and 95% CI	SAC
Urine/Faeces					
2.17.	PK	PK02	Summary of Urinary and Faecal –Total Radioactivity Pharmacokinetic Parameters (Amount Excreted) by Treatment and Time	Include Ae(urine), Ae(faeces) and Ae(total).	SAC
2.18.	PK	PK02	Summary of Urinary and Faecal –Total Radioactivity Pharmacokinetic Parameters (Cumulative Amount Excreted) by Treatment and Time	Include cumulative Ae(urine), Cumulative Ae(faeces) and Cumulative Ae(total).	SAC
2.19.	PK	PK02	Summary of Urinary and Faecal –Total Radioactivity Pharmacokinetic Parameters (% of Dose Excreted) by Treatment and Time	Include Fe%(urine), Fe%(faeces) and Fe%(total).	SAC
2.20.	PK	PK02	Summary of Urinary and Faecal –Total Radioactivity Pharmacokinetic Parameters (Cumulative % of Dose Excreted) by Treatment and Time	Include cumulative Fe%(urine), Cumulative Fe%(faeces) and Cumulative Fe%(total).	SAC

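### The SAP's Fg is labelled as gut-wall loss but calculated and used as gut-wall escape, and it carries hepatic first pass that Fabs then divides out a second time

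*SAP*

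**What the plan says.** SAP Table 1 (Section 8.1.2) builds five linked quantities.

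- ML(iv), introduced by "Metabolite load following intravenous administration is calculated as", is (total radioactivity AUC − parent AUC) / total radioactivity AUC in Period 1.
- ML(po), introduced by "Metabolite load following oral administration is calculated as", is the same fraction in Period 2.
- Fg, introduced by "Fraction metabolised by gut wall as a fraction of the oral dose will be calculated as follows", is 1 − (ML(po) − ML(iv)).
- E_H is CL(iv) / 1450 mL/min.
- Fabs, introduced by "Fraction absorbed following an oral dose is calculated as follows", is [Oral F(0–∞) / (1 − E_H)] / Fg.

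Section 8.3.2 gives their purpose: "To assess metabolism, the plasma PK parameters: ML(iv), ML(po), F g , E H , F abs will be summarised and listed". They are reported in Table 2.14, "Summary of Metabolic, Hepatic Extraction and Absorption Parameters", and in Listing 38. They are not protocol endpoints; the note in SAP Section 2.2 says "subsequently additional PK parameters have been requested including" these quantities. Section 11.4.3 assigns Fg and Fabs to the study programmer.

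**The concern.** There are two faults.

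**Label.** Fg as written equals 1 when the oral and IV metabolite loads are equal, and it falls as the oral load rises. Its description says the opposite. Someone reading Table 2.14 would take a value near 1 as near-complete gut-wall loss. The stated denominator is also inaccurate: ML is a fraction of circulating radioactivity AUC and does not depend on how much of the oral dose was absorbed.

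**Content.** The IV dose bypasses both gut and liver first pass; the oral dose meets both. The difference ML(po) − ML(iv) therefore contains liver loss, and nothing removes it before Fabs divides by 1 − E_H.

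At stake is the split between incomplete absorption, gut-wall loss and liver loss. Protocol Section 5.4 uses the oral dose as a surrogate for the swallowed part of an inhaled dose, so this split is what the added parameters are for.

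**Working it through.** The documents give no value for Fg, E_H or Fabs, so there is no planned figure to reproduce. The check puts known truths through the SAP formulas.

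**Assumptions (not in the documents).** Linear PK; all absorbed drug is eventually metabolised; the same metabolite AUC per unit formed by either route. Let x be the metabolite:parent AUC ratio after IV, fa the true fraction absorbed, fg the true fraction escaping the gut wall, and fh = 1 − E_H.

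**Algebra.**

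- ML(iv) = x / (x + 1)
- ML(po) = x / (x + fg·fh)
- Oral F = fa·fg·fh
- Planned Fabs / true fa = fg / [1 − (ML(po) − ML(iv))]

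The planned Fg sees only the product fg·fh.

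**Worked case: no gut loss.** Take fg = 1, E_H = 0.3, x = 1. ML(iv) = 1/2 = 0.500 and ML(po) = 1/1.7 = 0.588. Planned Fg = 1 − 0.088 = 0.912 instead of 1. Fabs / truth = 1/0.912 = 1.097, about 10% high.

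**Grid, x = 0.5 to 2.**

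| True fg | E_H | Planned Fg | Error in Fabs |
|---|---|---|---|
| 1 | 0.1 | 0.97–0.98 | +2 to +3% |
| 1 | 0.3 | 0.91–0.93 | +8 to +10% |
| 1 | 0.5 | 0.83–0.87 | +15 to +20% |
| 1 | 0.7 | 0.71–0.80 | +25 to +41% |
| 0.8 | 0.3 | 0.86–0.88 | −7 to −10% |
| 0.8 | 0.5 | 0.78–0.83 | −4 to +3% |
| 0.5 | 0.3 | 0.75–0.82 | −33 to −39% |

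Over the full grid (fg 1, 0.8, 0.5; E_H 0.1 to 0.7) planned Fabs / truth runs from 0.59 to 1.41. Two effects oppose each other. Counting liver loss twice raises Fabs. Taking a difference of two fractions understates real gut loss, which lowers Fabs.

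**Independent check.** A linear compartment model (central parent, liver, metabolite) with exact AUCs agrees. With true fg 1, fa 0.5, ML(iv) 0.5 and E_H 0.4, planned Fg is 0.875 and Fabs 0.571 (+14%). With fa 0.95 and E_H 0.4, Fabs is 1.02–1.09 for ML(iv) between 0.2 and 0.8, which is above 1.

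**Which way the label must be read.** With true fg 0.8, fa 0.5, E_H 0.4 and ML(iv) 0.5, the planned Fg is 0.824. Read as labelled, that is 82% metabolised when the truth is 20%. If the labelled quantity (0.176) went into Fabs, the result would be 0.24/0.6/0.176 ≈ 2.28, which is impossible. The formula must mean the escaping fraction.

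**Plausible E_H.** Protocol Section 5.5.1 predicts "3.5 ng/mL and 14.7 ng.h/mL for Period 1" (Cmax and AUC(0–24 h)). Taking 1000 µg / 14.7 ng·h/mL gives about 1134 mL/min apparent clearance. Assumed inhaled bioavailability of 0.2 to 1.0 gives CL of 227–1134 mL/min and E_H of 0.16–0.78. This is rough and errs high, because the AUC stops at 24 h.

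**The case against.** - **The label changes no computed number.** This stands. The formula and its use in Fabs are explicit, so code written from them gives the same output under either description. The label is a fault of interpretation, not a source of bias.
- **Only supportive parameters are touched.** This stands. ML(iv), ML(po), E_H, the parent/total-radioactivity ratios, CL(iv), Oral F and the primary endpoints do not use Fg. Listings 37 and 38 give the inputs per subject, so Fg can be recomputed later. A reader might infer that the metabolism assessment as a whole, or the bioavailability result, is compromised; the SAP's formulas do not support that.
- **The error can be small.** This stands. It is 2–3% at E_H 0.1 with no gut loss, within −4% to +3% at fg 0.8 and E_H 0.5, and 3.5% at x = 0.1, fg = 1, E_H 0.3. E_H 0.7 would need inhaled bioavailability of about 0.7 × 1450 / 1134 ≈ 0.9, so the 25–41% row is near the upper end. A reader might also infer that Fabs will always be too high. It will not: the direction reverses once gut loss is real.
- **The natural replacement is fragile.** This stands, and it limits the remedy. SAP Section 8 expects oral parent by LC/MS and total radioactivity by AMS, so ML(po) is a difference across two assays. With an assumed ±10% bias in oral parent AUC, true fg 1 and E_H 0.3, the replacement Fg runs 0.79–1.28 at x = 0.5, 0.67–1.69 at x = 0.2 and 0.53–3.67 at x = 0.1. The planned Fg runs 0.86–0.98, 0.87–1.02 and 0.88–1.05.
- **The replacement is inexact with renal clearance.** This stands, because E_H uses total CL(iv). In one example with 10 L/h renal clearance, it gave Fg 1.11 and Fabs 0.557 against truths of 1 and 0.5.

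None of this removes the contradiction in the label or the second removal of liver loss.

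**Conclusion.** The concern holds for Fg and Fabs only. The label contradicts the formula on the SAP's own text, with no PK assumption needed. The second fault follows from the definitions: whenever E_H is above zero, the planned Fg is below 1 even with no gut-wall metabolism, and Fabs corrects for the liver again. Error-free data would still give a biased Fabs, by anything from a negligible amount to roughly 40% in either direction over the assumed ranges. The size and sign cannot be fixed from the documents, since E_H, x and fg are unknown. The matter should be corrected before the parameters are programmed, but it does not threaten the study's main results.

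**What to change.** 1. Relabel Fg as the fraction escaping gut-wall metabolism, and delete the reference to the oral dose as its denominator.
2. Do not report 1 − (ML(po) − ML(iv)) as gut availability alone, and do not combine it with 1/(1 − E_H). Derive instead

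   Fg = {[(1 − ML(po)) / ML(po)] / [(1 − ML(iv)) / ML(iv)]} / (1 − E_H)

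   and keep Fabs = Oral F / [(1 − E_H) × Fg]. The term in braces equals (fg·fh/x) / (1/x) = fg·fh, so Fg returns fg under the assumptions above. Fabs then reduces to the oral/IV ratio of dose-normalised (total radioactivity − parent) AUC and no longer depends on E_H.
3. State the assumptions: linear PK, clearance essentially all by hepatic metabolism, and equal metabolite AUC per unit formed by either route. Check the second against CLr. That check needs parent drug in urine, which SAP Section 8.3.2 treats as conditional; Table 2 defines Ae[urine] as total radioactivity.
4. Report Fg and Fabs as not estimable when ML(iv) or ML(po) is near or below zero, with the cut-off set in advance, and show ML(iv), ML(po), E_H and Oral F alone in those cases.

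The cost is a wording change and one reprogrammed formula (Fg, which feeds Fabs) from AUCs already derived. The price is instability at low metabolite load, so some participants may have no Fg or Fabs value.

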5.5. Dose Justification

5.5.1. GSK2269557 Dose

This study will test single doses of GSK2269557, administered via different routes to healthy volunteers, in order to characterise the ADME properties of GSK2269557 in human. GSK2269557 is being developed for inhaled delivery and has been administered via inhalation at higher doses (6400 µg via nebulisation) than those proposed in this study (1000 µg). GSK2269557 has also been administered via inhalation, using the Diskus device, as a repeated dose of 1000 µg for 84 days to patients experiencing an exacerbation of COPD (study 116678). The inhaled dose of 1000 µg proposed in this study has been chosen to match the clinical material (device and formulation) for phase 2b and beyond, and to give a sufficient single dose to aid quantification of analytes.

The intravenous and oral dose routes have not previously been tested in humans, although testing has been conducted in pre-clinical studies. One of the purposes of the intravenous data is to define plasma pharmacokinetics and, in particular, central clearance rate from plasma. The proposed intravenous dose of 10 µg (given over a 15 minute infusion) represents less than 0.2% of the highest dose tested in humans (6400 µg) and is therefore expected to be well within the exposures generated previously. This includes the concomitant cold inhaled dose at 1000 µg. Due to absorption or first passes clearance effects; the oral dose of 800 µg is not expected to achieve systemic exposures close to those of an equivalent inhaled dose. However, based on previous data generated in humans using charcoal block (study 201544), exposure via this route is expected. In this study, approximately 23% of the systemic exposure of an inhaled 200 µg dose was attributable to the orally absorbed drug.

Table 1 shows the approximate estimates for exposures to participants following both treatment periods 1 and 2 using pharmacokinetic information obtained to date using a range of assumptions as detailed in the table. Systemic exposure multiples have been calculated based on both pre-clinical data and clinical experience with GSK2269557.

Table 1 Approximate estimates for exposures to participants

Period/Regimen	Parameter ¹	Exposure Margin	
		Pre-clinical ²	Clinical ³
1 = 1000 µg Inhaled + 10 µg IV	C _{max} (ng/mL)	13	2
	AUC _{0-24h} (ng.h/mL)	19	6
2 = 800 µg Oral	C _{max} (ng/mL)	94	11
	AUC _{0-24h} (ng.h/mL)	78	23

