Oral F (0-t)	
Oral absolute bioavailability based on AUC(0-t) calculated as:
 $\frac{\text{GSK2269557 AUC(0-t) (oral)}}{\text{Dose (oral)}} \Bigg/ \frac{[14\text{C}]\text{-GSK2269557 AUC(0-t) (iv)}}{\text{Dose (iv)}}$ 
Per subject.
 
Note: Radiometric dose will be used for oral and iv as described in Table 1.. GSK2269557 AUC(0-∞)(oral) may be updated depending on the sample analysis conducted but refers to the parent GSK2269557 from oral dose.

Inhaled F (0-t)	
Inhaled absolute bioavailability based on AUC(0-t) calculated as
 $\frac{\text{GSK2269557 AUC(0-t) (oral)}}{\text{Dose (oral)}} \Bigg/ \frac{[14\text{C}]\text{-GSK2269557 AUC(0-t) (iv)}}{\text{Dose (iv)}}$ 
Per subject.
 
Note: Radiometric dose will be used for oral and iv as described in Table 1.

GSK2269557 /Total radioactivity ratio for Cmax,	
Cmax Ratio = <math>\text{Exp} \{ [\text{log}(GSK2269557 \text{ Cmax})] - [\text{log}(\text{Total radioactivity Cmax})] \}</math>
 
Per subject for radiolabelled oral dose. GSK2269557 may be updated depending on the sample analysis conducted but refers to the parent GSK2269557 from oral dose

GSK2269557 /Total radioactivity ratio for AUC(0-inf)	
AUC(0-inf) Ratio = <math>\text{Exp} \{ [\text{log}(GSK2269557 \text{ AUC(0-inf)})] - [\text{log}(\text{Total radioactivity AUC(0-inf)})] \}</math>
 
Per subject for radiolabelled oral dose. GSK2269557 may be updated depending on the sample analysis conducted but refers to the parent GSK2269557 from oral dose

GSK2269557 /Total radioactivity	
AUC(0-t) Ratio = <math>\text{Exp} \{ [\text{log}(GSK2269557 \text{ AUC(0-t)})] - [\text{log}(\text{Total radioactivity AUC(0-t)})] \}</math>

Parameter	Parameter Description
ratio for AUC(0-t)	Per subject for radiolabelled oral dose. GSK2269557 may be updated depending on the sample analysis conducted but refers to the parent GSK2269557 from oral dose
[  C]-GSK2269557 /Total radioactivity ratio for Cmax,	Cmax Ratio = Exp { [loge([  C]-GSK2269557 Cmax] - [loge(Total radioactivity Cmax]) } Per subject for radiolabelled IV dose.
[  C]-GSK2269557 /Total radioactivity ratio for AUC(0-inf)	AUC(0-inf) Ratio = Exp { [loge([  C]-GSK2269557 AUC(0-inf)] - [loge(Total radioactivity AUC(0-inf)) } Per subject for radiolabelled IV dose.

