### 11.4.3. Reporting Standards for Pharmacokinetic

Pharmacokinetic Concentration Data	
PC Windows Non-Linear (WNL) File	PC WNL file (CSV format) for the non compartmental analysis by Clinical Pharmacology Modelling and Simulation function will be created according to PKOne. Note: Concentration values will be imputed as per GUI_51487
Descriptive Summary Statistics, Graphical Displays and Listings	Refer to IDSL PK Display Standards. Refer to IDSL Statistical Principle 6.06.1. Note: Concentration values will be imputed as per GUI_51487 for descriptive summary statistics/analysis and summarized graphical displays only.
Pharmacokinetic Parameter Derivation	
Plasma PK Parameter to be Derived by Programmer	The following PK parameters will be derived by the Programmer: CL r , ML(iv), ML(po), F g , E H , F abs , F(Oral, (0-t)), F(Oral, (0-∞)), F(inhaled, (0-t)), F (inhaled, (0-∞)) and the Parent GSK2269557/ Total Radioactivity ratio for Cmax, AUC(0-t), AUC(0-24) and AUC(0-∞). note: Parent GSK2269557/ Total Radioactivity ratios will be either GSK2269557/ Total Radioactivity or [14C]-GSK2269557/ Total Radioactivity depending on the method of sample analyses and are of interest for the radiolabelled IV and oral dose.
Urine and Faeces PK Parameter to be Derived by Programmer	The following PK parameters will be derived by the Programmer: cumulative Ae, Fe% and cumulative Fe%.
Pharmacokinetic Parameter Data	
Is NQ impacted PK Parameters Rule Being Followed	No.
Descriptive Summary Statistics, Graphical Displays and Listings	Refer to IDSL PK Display Standards. Refer to PKOne

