2.8.	PK	PK05	Summary of Log-Transformed Derived Plasma [14C]-GSK2269557 PK Parameters by Treatment	
Include columns for parameter, period, treatment, N, n, geometric mean, 95% CI of geometric mean, standard deviation (SD) of logged data, median, minimum, maximum and between subject geometric coefficient of variation (CVb (%)).
 
Refer to Section 11.4.3 for parameters that should be log transformed. In addition to standard [14C]-GSK2269557 pk parameters include Clearance (CL(iv) and CLr) and volume (Vdss and Vc).
 
refer to  gsk2269557/pii115119/part_a/drivers/t_pk_sum_log (Table 4.3)
	SAC
2.9.	PK	PK01	Summary of Plasma GSK2269557 Concentrations by Treatment and Time	Include untransformed concentrations	SAC
2.10.	PK	Refer to Programming Notes	Summary of Log Transformed Plasma GSK2269557 Concentrations by Treatment and Time	Include log transformed concentrations use standard macro for sumstatsinrows for log transformed variable, present similar to example shell PK01 but present geometric mean and SD (Log) rather than mean and SD respectively.	SAC
2.11.	PK	PK03	Summary of Derived Plasma GSK2269557 PK Parameters by Treatment	Include columns for parameter, period, treatment, N, n, arithmetic mean, 95% CI of arithmetic mean, standard deviation (SD), median, minimum and maximum.	SAC

Pharmacokinetic: Tables					
No.	Population	IDSL / TST ID / Example Shell	Title	Programming Notes	Deliverable
2.12.	PK	PK05	Summary of Log-Transformed Derived Plasma GSK2269557 PK Parameters by Treatment	
Include columns for parameter, period, treatment, N, n, geometric mean, 95% CI of geometric mean, standard deviation (SD) of logged data, median, minimum, maximum and between subject geometric coefficient of variation (CVb (%)).
 
Refer to Section 11.4.3 for parameters that should be log transformed
 
refer to gsk2269557/pii115119/part_a/drivers/t_pk_sum_log (Table 4.3)
	SAC
2.13.	PK	PK06	Summary of Oral and Inhaled Absolute Bioavailability	
Refer to Section 11.4.3 for parameters that should be log transformed.
 
Include PK Parameters: Inhaled F (0-∞), Inhaled F (0-t), Oral F (0-∞) and Oral F (0-t), Dose(Inhaled), Dose(iv) and Dose(Oral).
 
Note: Dose(iv) and Dose(Oral) is radiometric dose, Dose(Inhaled) is nominal
	SAC

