### 11.9.9. Non-ICH Listings

Non-ICH: Listings					
No.	Population	IDSL / TST ID / Example Shell	Title	Programming Notes	Deliverable
Plasma PK					
31.	PK	PK08	Listing of Plasma Total Radioactivity-Time Data		SAC
32.	PK	PK14	Listing of Derived Plasma Total Radioactivity Pharmacokinetic Parameters		SAC
33.	PK	PK08	Listing of Plasma [14C]-GSK2269557 Concentration-Time Data		SAC
34.	PK	PK14	Listing of Derived Plasma [14C]-GSK2269557 Pharmacokinetic Parameters	In addition to standard [14C]-GSK2269557 pk parameters include Clearance (CL(iv) and CLr) and volume (Vdss and Vc).	SAC
35.	PK	PK08	Listing of Plasma GSK2269557 Concentration-Time Data		SAC
36.	PK	PK14	Listing of Derived Plasma GSK2269557 Pharmacokinetic Parameters		SAC
37.	PK	PK14	Listing of Oral and Inhaled Absolute Bioavailability	Include PK Parameters: Inhaled F (0-∞), Inhaled F (0-t), Oral F (0-∞) and Oral F (0-t), Dose(Inhaled), Dose(iv) and Dose(Oral).  Note: Dose(iv) and Dose(Oral) is radiometric dose, Dose(Inhaled) is nominal	SAC
38.	PK	PK14	Listing of Metabolic, Hepatic Extraction and Absorption Parameters	Include PK Parameters: ML(iv), ML(po), F g , E H and F abs	SAC
39.	PK	PK15	Listing of Individual Subject Parent GSK2269557/Total Radioactivity Ratio for Cmax, AUC(0-∞), AUC(0-24) and AUC(0-t)		SAC

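### The SAP's formula for Inhaled F(0-t) is the Oral F(0-t) formula, so programmed as written it reports oral bioavailability under the inhaled label

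*SAP*

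**What the plan says.** Oral and inhaled absolute bioavailability is a secondary endpoint (Protocol Section 4; SAP Section 2.2). The SAP reports each route in two versions, one on AUC(0-∞) and one on AUC(0-t).

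SAP Table 1 in Section 8.1.2 gives the formulas. The oral AUC(0-t) row reads "Oral absolute bioavailability based on AUC(0-t) calculated as: $\frac{\text{GSK2269557 AUC(0-t) (oral)}}{\text{Dose (oral", divided by the IV term. The inhaled AUC(0-t) row reads "Inhaled absolute bioavailability based on AUC(0-t) calculated as $\frac{\text{GSK2269557 AUC(0-t) (oral)}}{\text{Dose (oral", divided by the same IV term. The inhaled AUC(0-∞) row uses inhaled quantities in its numerator: "GSK2269557 AUC(0-∞) (inhaled)}}{\text{Dose (inhaled". The same table defines Dose(inhaled) as the nominal inhaled dose.

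SAP Section 11.4.3 gives these derivations to the programmer, naming "F(Oral, (0-t)), F(Oral, (0-∞)), F(inhaled, (0-t)), F (inhaled, (0" and its closing term, with no other formula. For Table 2.13, SAP Section 11.9.5 instructs: "Include PK Parameters: Inhaled F (0-∞), Inhaled F (0-t), Oral F (0-∞) and Oral F (0-t), Dose(Inhaled), Dose(iv) and Dose(Oral". The corresponding listing is number 37, "Listing of Oral and Inhaled Absolute Bioavailability".

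**The concern.** A row labelled and described as inhaled bioavailability contains no inhaled quantity. If the formula is coded as it stands, the Inhaled F(0-t) line of Table 2.13 and Listing 37 will hold oral bioavailability, printed beside a Dose(Inhaled) that was not used to compute it.

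The analyte name gives no protection. SAP Section 8 expects the inhaled parent drug in period 1 and the oral parent drug in period 2 both to be measured by LC/MS and both to be labelled GSK2269557. Only the route tag separates the two AUCs, and the route tag is what is wrong. A second programmer checking from the same specification would get the same wrong number.

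The AUC(0-t) version is not merely decorative. Section 8.1.2 derives parameters only as data permit, and the renal clearance row of Table 1 already provides for AUC(0-∞) not being calculable. In a participant for whom that happens, F(0-t) would be the only inhaled estimate, and it would be the oral one.

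**Working it through.** **Formulas side by side (SAP Table 1)**

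| Row | Numerator | Denominator |
|---|---|---|
| Inhaled F(0-∞) | AUC(0-∞)(inhaled) / Dose(inhaled) | [14C] AUC(0-∞)(iv) / Dose(iv) |
| Oral F(0-t) | AUC(0-t)(oral) / Dose(oral) | [14C] AUC(0-t)(iv) / Dose(iv) |
| Inhaled F(0-t), as written | AUC(0-t)(oral) / Dose(oral) | [14C] AUC(0-t)(iv) / Dose(iv) |

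A character comparison of the last two expressions finds them identical. So Inhaled F(0-t) = Oral F(0-t) in every participant, whatever the data. This step needs no assumption.

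**Scale**

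The documents state no bioavailability figure to reproduce, so the size can only be illustrated from the planning exposures. The IV term is common to both values and cancels:

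intended / printed = [AUC(inhaled) / 1000 µg] / [AUC(oral) / 800 µg]

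Inputs, all from Protocol Section 5.5.1 and footnote 1 to its Table 1:

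- predicted AUC(0-24h): 14.7 ng.h/mL in period 1 and 3.7 ng.h/mL in period 2;
- IV exposure taken as 1% of inhaled exposure;
- a formulation factor of 1.54 on AUC;
- the oral share: "approximately 23% of the systemic exposure of an inhaled 200 µg dose was attributable to the orally absorbed drug";
- the deposition split: "assuming 60:40 lung to oral deposition using study data from 201544 and charcoal block and linear extrapolation".

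Inhaled: 14.7 / 1.01 = 14.55 ng.h/mL, or 0.01455 per µg.

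Oral, three readings:

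- (a) Stated prediction: 3.7 / 800 = 0.00463 per µg. Ratio 0.01455 / 0.00463 = 3.15; printed/intended = 0.32. Rounding of 14.7 and 3.7, and whether the 1% IV part is removed, moves the ratio between 3.09 and 3.23.
- (b) 23% of 14.55 coming from 400 µg swallowed, divided by 1.54: 0.23 × 14.55 / 400 / 1.54 = 0.00543 per µg. Ratio 2.68; printed/intended = 0.37.
- (c) As (b) without the 1.54: 0.23 × 14.55 / 400 = 0.00837 per µg. Ratio 1.74; printed/intended = 0.58.

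Readings (b) and (c) imply oral AUCs of 4.35 and 6.70 ng.h/mL for 800 µg, about 18% and 81% above the protocol's 3.7. They mark how far the ratio could fall on the protocol's other inputs. Only (a) rests on exposures that the protocol states.

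**The case against.** The strongest reply is that this is a copying slip whose intent nobody could mistake. The row's label and description both say inhaled, the AUC(0-∞) row is right, and Dose(inhaled) has its own definition. Two matching rows in one table would probably be noticed. The protocol does not name an AUC(0-t) version of F. Inhaled F(0-∞) still delivers the endpoint wherever AUC(0-∞) can be calculated. No hypothesis is tested, the primary objectives are untouched, and F(0-t) could be recomputed from the reported AUCs and doses.

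Much of that is true, and it limits the consequence. It does not make the formula right. The programmer is told to derive this parameter and has only this formula. Relying on someone to notice the coincidence later is weaker than correcting the line.

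The objection to the range has force. It substitutes predicted AUC(0-24h) for AUC(0-t) although sampling runs to 168 h, and its lower end depends on constructions that do not reproduce the protocol's own oral prediction. The ratios are illustrations; the identity of the two formulas does not depend on them.

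Two further points do not change the conclusion. The SAP text was machine-read from PDF, so the page itself should be checked. A reading error is unlikely, because the two rows carry different notes and the inhaled terms were read correctly in the AUC(0-∞) row. Separately, the SAP takes t as the last quantifiable concentration, while the protocol's abbreviation list takes it within a participant across all treatments. That deserves its own clarification but bears on neither the error nor its correction.

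**Conclusion.** The concern holds. As written, Inhaled F(0-t) equals Oral F(0-t) exactly, in every participant, and no other part of the SAP supplies a correct formula. The error is confined to that one parameter and its appearances in Table 2.13 and Listing 37. Inhaled F(0-∞), both oral values and the fraction absorbed, which is built on Oral F(0-∞), are unaffected.

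On the protocol's stated predictions the printed figure would be about a third of the intended one (ratio 3.15). This assumes that predicted AUC(0-24h) stands in for AUC(0-t) and that the protocol's linear extrapolation and 1% IV share hold. On the looser readings it would be up to 58%. Because a secondary-endpoint parameter is wrongly defined and the correction is unambiguous, it should be made before programming.

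**What to change.** In SAP Table 1, replace the Inhaled F(0-t) formula with:

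[GSK2269557 AUC(0-t)(inhaled) / Dose(inhaled)] / [[14C]-GSK2269557 AUC(0-t)(iv) / Dose(iv)]

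This matches the Inhaled F(0-∞) row, with Dose(inhaled) the nominal dose and Dose(iv) the radiometric dose as already defined. If any code has been written from the present table, check that it takes the period 1 inhaled AUC and Dose(inhaled). The cost is one line of SAP wording, with no new data, samples or analyses.
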